11.2. Procedures for Reporting Adverse Events and Serious Adverse Events

All AEs (serious and non-serious) spontaneously reported by the subject and/or in response to an open question from study personnel or revealed by observation, physical examination, or other diagnostic procedures will be recorded on the appropriate page of the eCRF. Any clinically relevant deterioration in laboratory assessments or other clinical findings is considered an AE and must be recorded on the appropriate pages of the eCRF.

For reports of SAEs, Investigators should record all case details that can be gathered promptly on both the AE and the SAE eCRFs and submit via the Electronic Data Capture (EDC) system. All SAEs are to be reported within 24 hours from the point in time when the Investigator becomes aware of the SAE. All SAEs must be reported whether or not they are considered causally related

to AG-120/placebo. Serious AE forms will be completed and the information collected will include subject number, a narrative description of the event, and an assessment by the Investigator as to the severity of the event and relatedness to study drug. Follow-up information on the SAE may be requested by the Sponsor or Medical Monitor.

In the event that the EDC system is unavailable, a paper SAE and fax coversheet should be completed and faxed/emailed within no more than 24 hours after learning of the event using the fax numbers provided to Investigators in the safety reporting instructions. The information from the SAE report form should be entered into the EDC system as soon as it is available.

If there are serious, unexpected related AEs associated with the use of AG-120/placebo, the Sponsor will notify the appropriate regulatory agency(ies) and all participating Investigators on an expedited basis. The local Institutional Review Board/Independent Ethics Committee (IRB/IEC) will be promptly notified based on local regulations where required by the IRB/IEC of all serious, unexpected related AEs involving risk to human subjects.

Anticipated SAEs

The Sponsor does not plan to report individually, in an expedited manner, specific serious, frequent AEs because these events are anticipated to occur in the study population at some frequency independent of drug exposure.

These SAEs include the following AML-specific manifestations:

- Neutropenia
- Thrombocytopenia
- Anemia
- Viral, bacterial, and fungal infections

All AEs, whether serious or not, will be described in the source documents and on the AE page of the eCRF. All new events, as well as those that worsen in severity or frequency relative to baseline, which occur after subjects have received at least 1 dose of study treatment through 28 days following the last dose of study treatment, must be recorded. Adverse events that are ongoing at the time of treatment discontinuation should be followed through the 4-week (28-day) post-treatment assessment. In addition, SAEs that are assessed by the Investigator as related to study drug must be reported any time the Investigator becomes aware of such an event, even if this occurrence is more than 28 days after the last dose of study treatment.

Information to be reported in the description of each AE includes:

- A medical diagnosis of the event (if a medical diagnosis cannot be determined, a description of each sign or symptom characterizing the event should be recorded).
- The date of onset of the event.
- The date of resolution of the event.
- Whether the event is serious or not.
- Severity of the event (see below for definitions).
- Relationship of the event to study treatment (see [Table 12](#) for definitions).

- Action taken: none; change in the study treatment administration (eg, temporary interruption in dosing); drug treatment required; non-drug treatment required; hospitalization or prolongation of hospitalization required (complete SAE page); diagnostic procedure performed; subject discontinued from study treatment (complete EOT Visit).
- Outcome: subject recovered without sequelae; subject recovered with sequelae; event ongoing; subject died (notify the Medical Monitor within 24 hours, and complete the SAE form).

Severity of all AEs, including clinically significant treatment-emergent laboratory abnormalities, will be graded according to the NCI CTCAE version 4.03 (see Appendix 15.9). Adverse events not listed by the CTCAE will be graded as follows:

- Mild: The event is noticeable to the subject but does not interfere with routine activity.
- Moderate: The event interferes with routine activity but responds to symptomatic therapy or rest.
- Severe: The event significantly limits the subject's ability to perform routine activities despite symptomatic therapy.
- Life-threatening: An event in which the subject was at risk of death at the time of the event.
- Fatal: An event that results in the death of the subject.

11.2.1. Diagnosis Versus Signs and Symptoms

A diagnosis (if known) should be recorded on the Adverse Event eCRF rather than individual signs and symptoms (eg, record only liver failure or hepatitis rather than jaundice, asterixis, and elevated transaminases). However, if a constellation of signs and/or symptoms cannot be medically characterized as a single diagnosis or syndrome at the time of reporting, each individual event should be recorded on the Adverse Event eCRF. If a diagnosis is subsequently established, all previously reported AEs based on signs and symptoms should be nullified and replaced by 1 AE term based on the single diagnosis, with a starting date that corresponds to the starting date of the first symptom of the eventual diagnosis.

11.2.2. Adverse Events Occurring Secondary to Other Events

In general, AEs occurring secondary to other events (eg, cascade events or clinical sequelae) should be identified by their primary cause, with the exception of severe or serious secondary events. However, medically significant AEs occurring secondary to an initiating event that are separated in time should be recorded as independent events on the Adverse Event eCRF. For example:

- a. If vomiting results in mild dehydration with no additional treatment in a healthy adult, only vomiting should be reported on the eCRF.
- b. If vomiting results in severe dehydration, both events should be reported separately on the eCRF.

- c. If a severe gastrointestinal hemorrhage leads to renal failure, both events should be reported separately on the eCRF.
- d. If dizziness leads to a fall and subsequent fracture, all 3 events should be reported separately on the eCRF.
- e. If neutropenia is accompanied by a severe or serious infection, both events should be reported separately on the eCRF.

All AEs should be recorded separately on the Adverse Event eCRF if it is unclear as to whether the events are associated.

11.2.3. Adverse Events of Special Interest

An AESI can be serious or non-serious and is an event of special interest to the Sponsor. Ongoing monitoring and rapid communication (within 24 hours) by the Investigator to the Sponsor is required to allow for further characterization and reporting to regulatory authorities.

11.2.3.1. QT Prolongation

Any QT prolongation event assessed as Grade ≥ 3 (ie, QTcF > 500 msec on at least 2 separate ECGs, or QTcF > 500 msec or ≥ 60 msec change from baseline with Torsade de pointes or polymorphic ventricular tachycardia or signs/symptoms of serious arrhythmia), irrespective of the seriousness, should be reported as an AESI to the Sponsor within 24 hours. See Section 9.9.1 for further details on managing subjects with QT prolongation. Heart-rate corrected QT interval will be calculated using Fridericia's formula ($QTcF = QT/RR^{1/3}$).

11.2.3.2. Leukocytosis

Any event of leukocytosis assessed as Grade ≥ 3 , irrespective of seriousness, should be reported to the Sponsor as an AESI within 24 hours.

See Section 9.13.4.3 for further details on managing subjects with leukocytosis.

11.2.3.3. IDH Differentiation Syndrome

Any event of differentiation syndrome assessed as Grade ≥ 2 , irrespective of seriousness, should be reported to the Sponsor as an AESI within 24 hours. See Section 9.9.2 for further details on managing subjects with differentiation syndrome.

11.2.4. Persistent or Recurrent Adverse Events

A persistent AE is 1 that extends continuously, without resolution, between subject evaluation time points. The initial severity of the event should be recorded, and the severity should be updated to reflect the most extreme severity any time the event worsens in intensity or grade.

When an AE becomes serious (regardless of changes in grade or severity), the eCRF should be updated to reflect this. As such, a new AE (serious event with onset date for when AE became serious) should be added to the eCRF.

However, the same does not hold true for AEs that change from serious to non-serious events. When an AE does not resolve but is downgraded from a serious to a non-serious event, a new AE is not required to be captured on the eCRF. A resolution date is required to be entered on the

SAE form once an AE changes from a serious to non-serious event since this would result in the SAE resolving.

A recurrent AE is 1 that resolves between subject evaluation time points and subsequently recurs. Each recurrence of an AE should be recorded separately on the Adverse Event eCRF.

11.2.5. Abnormal Laboratory Values

Not every laboratory abnormality qualifies as an AE. A laboratory test result should be reported as an AE if it meets any of the following criteria:

- a. Accompanied by clinical symptoms.
- b. Results in a change in study treatment (eg, dosage modification, treatment interruption, or treatment discontinuation).
- c. Results in a medical intervention (eg, potassium supplementation for hypokalemia) or a change in concomitant therapy.
- d. Clinically significant in the Investigator's judgment.

It is the Investigator's responsibility to review all laboratory findings. Medical and scientific judgment should be exercised in deciding whether an isolated laboratory abnormality should be classified as an AE.

If a clinically significant laboratory abnormality is a sign of a disease or syndrome (eg, ALP and bilirubin $5 \times$ ULN associated with cholecystitis), only the diagnosis (ie, cholecystitis) should be recorded on the Adverse Event eCRF.

If a clinically significant laboratory abnormality is not a sign of a disease or syndrome, the abnormality itself should be recorded on the Adverse Event eCRF, along with a descriptor indicating if the test result is above or below the normal range. Where possible, please enter a condition (eg, neutropenia) rather than the lab finding (eg, decreased neutrophils).

11.2.6. Deaths

Deaths occurring during the protocol-specified AE reporting period (see Section 11.2) that are attributed by the Investigator solely to progression of AML should be recorded only on the Treatment and/or Study Discontinuation eCRFs. All other on-treatment deaths, regardless of relationship to study treatment, must be recorded on the Adverse Event eCRF and reported to the Sponsor within 24 hours.

Death should be considered an outcome and not a distinct event. The underlying medical diagnosis or suspected diagnosis that caused or contributed to the fatal outcome should be recorded as the single medical concept on the Adverse Event eCRF. Generally, only 1 such event should be reported.

The term "sudden death" should only be used for the occurrence of an abrupt and unexpected death due to presumed cardiac causes in a subject with or without preexisting heart disease, within 1 hour of the onset of acute symptoms or, in the case of an unwitnessed death, within 24 hours after the subject was last seen alive and stable. If the cause of death is unknown and cannot be ascertained at the time of reporting, "unexplained death" should be recorded on the Adverse Event eCRF. If the cause of death later becomes available (eg, after autopsy), "unexplained death" should be replaced by the established cause of death.

All deaths will be collected. All on-treatment deaths (within the 28 days after last dose of study treatment) should have an associated SAE captured for the event that led to death, except in the event of disease progression (see Section 11.2.7).

During post-treatment survival follow-up, all deaths will continue to be collected, but only those unrelated to disease progression and considered related to study treatment by the Investigator will be captured as SAEs.

11.2.7. Progression of AML

Progression of AML (see Table 11) should not be reported as an AE if it is clearly consistent with the suspected progression of the underlying cancer. Clinical symptoms of progression may be reported as AEs if the symptoms cannot be determined as exclusively due to the progression of the subject's underlying AML or does not fit the expected pattern of progression for the disease.

If there is any uncertainty about an AE being due only to the disease under study, it should be reported as an AE or SAE.

11.2.8. Pre-existing Medical Conditions

A pre-existing medical condition is 1 that is present at the Screening Visit for this study. Such conditions should be recorded on the Medical History eCRF.

A preexisting medical condition should be recorded as an AE only if the frequency, severity, or character of the condition worsens during the study. When recording such events on the Adverse Event eCRF, it is important to convey the concept that the preexisting condition has changed by including applicable descriptors (eg, "more frequent headaches").

11.2.9. Hospitalization or Prolonged Hospitalization

Any AE that results in hospitalization or prolonged hospitalization should be documented and reported as an SAE (per the definition of SAE in Section 11.1.3), except as outlined below.

The following hospitalization scenarios are *not considered* to be SAEs:

- Hospitalization for respite care.
- Standard procedure for protocol therapy administration; however, hospitalization or prolonged hospitalization for a complication of therapy administration will be reported as an SAE.
- Routine treatment or monitoring of the studied indication not associated with any deterioration in condition.
- Administration of blood or platelet transfusion as routine treatment of studied indication; however, hospitalization or prolonged hospitalization for a complication of such transfusion remains a reportable SAE.
- A procedure for protocol/disease-related investigations (eg, surgery, scans, endoscopy, sampling for laboratory tests, bone marrow sampling); however, hospitalization or prolonged hospitalization for a complication of such procedures remains a reportable SAE.

- Hospitalization or prolongation of hospitalization for technical, practical, or social reasons, in absence of an AE.
- A procedure that is planned (ie, planned prior to start of treatment on study); must be documented in the source document and the eCRF; hospitalization or prolonged hospitalization for a complication remains a reportable SAE.
- An elective treatment of or an elective procedure for a pre-existing condition, unrelated to the studied indication, which has not worsened from baseline.

11.2.10. Overdose or Incorrect Administration

Study treatment overdose is the accidental or intentional use of the drug in an amount higher than the dose being studied. An overdose or incorrect administration of study treatment is not an AE unless it results in untoward medical effects.

Any study treatment overdose or incorrect administration of study treatment should be noted on the Study Drug Administration eCRF.

All AEs associated with an overdose or incorrect administration of study treatment should be recorded on the Adverse Event eCRF. If the associated AE fulfills serious criteria, the event should be reported to the Sponsor within 24 hours after learning of the event.

11.3. Pregnancy Reporting

Pregnancy is neither an AE nor an SAE, unless a complication relating to the pregnancy occurs (eg, spontaneous abortion, which may qualify as an SAE).

Pregnancies and suspected pregnancies (including a positive pregnancy test regardless of age or disease state) of a female subject or partner of a male subject occurring while the subject is on study treatment, or within 4 weeks (28 days) of the subject's last dose of study treatment, are considered immediately reportable events. If a female partner of a male subject taking investigational product becomes pregnant, the male subject taking study treatment should notify the Investigator, and the pregnant female partner should be advised to call her healthcare provider immediately. In pregnant female subjects, study treatment is to be discontinued immediately and the subject instructed to return any unused study drug to the Investigator. The pregnancy, suspected pregnancy, or positive pregnancy test must be reported immediately using the pregnancy report form. The Investigator must follow up and document the course and outcome of all pregnancies even if the subject was discontinued from the study or if the study has finished. The female subject or partner of a male subject should receive any necessary counseling regarding the risks of continuing the pregnancy and the possible effects on the fetus. Monitoring should continue until conclusion of the pregnancy.

All outcomes of pregnancy (from a female subject or the sexual partner of a male subject) must be reported by the Investigator to the Sponsor or Medical Monitor on a Pregnancy Outcome Report form within 4 weeks after he/she has gained knowledge of the delivery or elective abortion.

Any SAE that occurs during pregnancy must be recorded on the SAE report form (eg, maternal serious complications, spontaneous or therapeutic abortion, ectopic pregnancy, stillbirth,

neonatal death, congenital anomaly, or birth defect) and reported within 24 hours in accordance with the procedure for reporting SAEs.

Females of reproductive potential must have a negative serum pregnancy test prior to the start of therapy, or a confirmation from an obstetrician in case of equivocal serum pregnancy results. Women of reproductive potential, as well as fertile men with partners who are female with reproductive potential, must agree to use 2 effective forms of contraception (including 1 barrier form) from the time of giving informed consent, during the study, and for 90 days (females and males) following the last dose of study drug. Females of reproductive potential are defined as sexually mature women who have not undergone a hysterectomy or bilateral oophorectomy, or who have not been naturally postmenopausal (ie, who have not menstruated at all) for at least 24 consecutive months (ie, has had menses at any time in the preceding 24 consecutive months).

Males with partners who are female with reproductive potential must agree that they or their partners will use at least 2 effective contraceptive methods (including 1 barrier method) when engaging in reproductive sexual activity throughout the study, and will avoid conceiving for 90 days after the last dose of study treatment.

An effective form of contraception is defined as hormonal oral contraceptives, injectables, patches, intrauterine devices, intrauterine hormone-release systems, bilateral tubal ligation, condoms with spermicide, or male partner sterilization. If not using an effective form of contraception, participants must use 2 of the following methods: progestogen-only hormonal contraception; male or female condom with or without spermicide; cap, diaphragm, or sponge with spermicide. Refer to Section 9.13.2 for potential drug-drug interactions with hormonal contraceptives.

Females of reproductive potential must undergo a urine pregnancy test to be conducted on C1D1 and confirmed negative prior to dosing, and on Day 1 of all subsequent cycles. The test should be conducted pre-dose, and these subjects should undergo a urine pregnancy test at the end of treatment visit.

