7. Have agreed to undergo serial blood and bone marrow sampling.
8. Be able to understand and willing to sign an informed consent form (ICF).
9. Be willing to complete QoL assessments during study treatment and at the designated time points following treatment discontinuation.
10. If female with reproductive potential, must have a negative serum pregnancy test prior to the start of study therapy. Female subjects with reproductive potential are defined as sexually mature women who have not undergone a hysterectomy, bilateral oophorectomy, or tubal occlusion or who have not been naturally postmenopausal for at least 24 consecutive months. Females of reproductive potential, as well as fertile men with female partners of reproductive potential, must use 2 effective forms of contraception (including at least 1 barrier form) from the time of giving informed consent throughout the study and for 90 days (both females and males) following the last dose of study drug(s). Effective forms of contraception are defined as hormonal oral contraceptives, injectables, patches, intrauterine devices, intrauterine hormone-releasing systems, bilateral tubal ligation, condoms with spermicide, or male partner sterilization. Coadministration of AG-120 may decrease the concentrations of hormonal contraceptives (Section 9.13.2).

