9.13.2. Concomitant Therapy Requiring Careful Monitoring

Concomitant use of drugs with a potential for QT prolongation should be avoided and replaced with alternative treatments. If this is not possible, subjects receiving these drugs should be adequately monitored by ECG controls, drug concentration (where applicable), and serum electrolytes (ie, potassium and magnesium). See Section 9.9.1 for guidance on managing QT prolongation.

These medications include, but are not limited to:

- Fluoroquinolones, such as ciprofloxacin and moxifloxacin.
- Azole antifungals, such as fluconazole and posaconazole.
- Serotonin (5-HT₃) antagonists, such as granisetron and ondansetron.

Other examples of drugs known to prolong the QT interval are listed in Appendix 15.5.

Systemic administration of moderate or strong CYP3A4 inhibitors (see Appendix 15.7) requires careful monitoring of QTcF.

Coadministration of AG-120 with narrow therapeutic index drugs that are extensively metabolized by CYP2C9 (eg, phenytoin, warfarin) may result in decreased concentrations of these drugs. Consider alternative therapies that are not sensitive substrates of CYP2C9 during

treatment with AG-120. Subjects should be monitored for loss of therapeutic effect of these medications if coadministration with AG-120/placebo cannot be avoided. Monitor international normalized ratio (INR) levels more frequently in subjects receiving warfarin during initiation or discontinuation of AG-120/placebo.

Coadministration of AG-120 may decrease the concentrations of hormonal contraceptives. Consider alternative methods of contraception in subjects receiving AG-120/placebo. Please refer to Inclusion Criterion 10 in Section 8.2 for contraception requirements.

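### Section 11.3 requires two effective forms of contraception, then allows a fallback that can contain no effective form under its own definition or under Inclusion Criterion 10

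*Protocol*

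**What the plan says.** Three parts of the Protocol set contraception rules.

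- **Section 11.3, base rule.** Women of reproductive potential, and fertile men with such partners, "must agree to use 2 effective forms of contraception (including 1 barrier form"), from consent until 90 days after the last dose. The term is then defined: "An effective form of contraception is defined as hormonal oral contraceptives, injectables, patches, intrauterine devices, intrauterine hormone-release systems, bilateral tubal ligation, condoms with spermicide", with male partner sterilization as the last item. That makes eight forms, and the wording leaves no room for others.
- **Section 11.3, fallback.** The next sentence reads "If not using an effective form of contraception, participants must use 2 of the following methods: progestogen-only hormonal contraception". Two further groups complete that second list, a condom with spermicide optional and a spermicide-treated cap, diaphragm or sponge.
- **Inclusion Criterion 10 (Section 8.2, repeated in the Synopsis).** It sets the same number of effective forms, with at least one barrier, over the same period. It defines the term by the same eight items: "Effective forms of contraception are defined as hormonal oral contraceptives, injectables, patches, intrauterine devices, intrauterine hormone-releasing systems, bilateral tubal ligation, condoms with spermicide", and again male partner sterilization. It offers no alternative route.

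Section 9.13.2 says which text controls: "Please refer to Inclusion Criterion 10 in Section 8.2 for contraception requirements".

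On pregnancy testing, Section 11.3 accepts an obstetrician's confirmation when the serum result is equivocal. Criterion 10 asks for a negative serum test before study therapy. Section 9.7, Section 10.6.5 and footnote 16 of Table 6 ask for a serum test shown to be negative within 72 hours before treatment. None of these four places has an exception.

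**The concern.** The fallback is addressed to people who are not using an effective form. The same section has just said that such people must use two. If the sentence has any effect, it is to permit contraception that the protocol does not itself class as effective.

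This is a patient-safety rule applied at up to 190 centers in 20 countries. A site that looks up contraception in Section 11.3 can, in good faith, give advice that a site reading Criterion 10 would not give. The exception for equivocal tests is a smaller case of the same kind: one section is looser than every other place where the rule appears.

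**Working it through.** The Protocol gives no figure to reproduce. The check takes each pair that the fallback permits and counts how many members are on the closed list, which is the same list in Section 11.3 and Criterion 10. The base rule needs two.

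**Inputs**

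- Listed forms: eight. The only barrier among them is a condom with spermicide.
- Fallback groups: (P) progestogen-only hormonal method; (C) condom, with or without spermicide; (D) cap, diaphragm or sponge, with spermicide.
- Overlap with the list: C counts only with spermicide. P counts only if it is taken in a listed form, such as a pill or an injectable. D never counts.

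**Pairs**

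| Pair | Variant | Listed forms (2 needed) | Barrier included |
|---|---|---|---|
| C + D | condom without spermicide | 0 | yes |
| C + D | condom with spermicide | 1 | yes |
| P + D | P not in a listed form | 0 | yes |
| P + D | P in a listed form | 1 | yes |
| P + C | P not listed, no spermicide | 0 | yes |
| P + C | P not listed, spermicide | 1 | yes |
| P + C | P listed, no spermicide | 1 | yes |
| P + C | P listed, spermicide | 2 | yes |

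**Reading the table**

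1. The first row is enough to prove the conflict. A condom without spermicide with a diaphragm satisfies the fallback and contains 0 effective forms where 2 are required.
2. At group level, C + D and P + D can never reach two listed forms, because D is not on the list.
3. Only the last row meets the base rule. A participant using that pair already complies and does not need the fallback.
4. Every row includes a barrier, so the conflict is about which methods count as effective, not about the barrier requirement.

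**Timing.** Criterion 10 runs from consent through 90 days after the last dose. It therefore cannot be read as an entry-only rule that Section 11.3 later relaxes.

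**The case against.** The strongest reply is that the protocol already settles the matter. All inclusion criteria must be met, Section 9.13.2 names Criterion 10 for contraception, and under Section 8.4 the Medical Monitor confirms every subject's eligibility before the first dose of AG-120 or placebo. The fallback sits under Pregnancy Reporting and cannot make anyone eligible. This stands, and it limits the consequence. It does not remove the contradiction inside Section 11.3. The Medical Monitor's check comes before dosing, while the contraception rule runs until 90 days after the last dose.

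A reader might also infer more than the documents support:

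- *That Criterion 10 rejects everything on the second list.* It does not. A condom with spermicide is on both lists, and some progestogen-only methods can fall under the listed pills or injectables.
- *That the share of failing rows measures the problem.* The table shows 7 of 8 short of two listed forms, but that depends on how methods are split. Counting cap, diaphragm and sponge separately gives 4 + 6 + 6 = 16 variants, of which 15 fall short. Without splitting, there are 3 pairs, of which 2 never comply. No document gives usage, so none of these is an effect size.
- *That the interaction with hormonal contraceptives makes the fallback worse.* It applies equally to hormonal methods that Criterion 10 accepts, and Section 11.3 points to it: "Refer to Section 9.13.2 for potential drug-drug interactions with hormonal contraceptives".
- *That the differing definitions of reproductive potential show Section 11.3 to be right or wrong.* Criterion 10 exempts women with tubal occlusion and Section 11.3 does not. Listing tubal ligation as a contraceptive form is still coherent under Criterion 10, because its rule also covers the female partners of male subjects. The documents do not settle which definition to keep.

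**Conclusion.** The point holds in a limited form. Section 11.3 permits some combinations with no effective form under its own definition or under Criterion 10, and so contradicts both. This rests on reading the two definitions as closed lists, which is how they are worded.

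It is a minor point, worth correcting because the rule protects subjects and the correction is easy. The documents do not support a claim that anyone could be enrolled under the looser standard, and they do not give the number of subjects affected. No efficacy analysis changes. The exception for equivocal serum tests is a smaller inconsistency: Section 11.3 is alone against Criterion 10, Sections 9.7 and 10.6.5, and Table 6.

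**What to change.** In Section 11.3, delete the sentence that introduces the fallback and refer to Inclusion Criterion 10 for contraception, as Section 9.13.2 already does. As a minor alignment, delete the obstetrician-confirmation exception, so that a negative serum test before dosing is the rule throughout.

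Adding the fallback to Criterion 10 would also make the texts agree. It would do so by bringing into the eligibility rule methods that the protocol does not class as effective, so deletion is the better choice.

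The cost is protocol wording only. Consent pages are not among the documents available, so any matching consent text should be checked at the same time.
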